6.5.1. Sensitivity Analyses

The primary analysis assumes that missing data are missing at random – i.e. the missingness depends only on the values of observed variables. This is an assumption which cannot be proven. Although we can show that missingness is related to values of observed variables (suggesting MAR and proving that MCAR does not hold), it is impossible to prove that there is no non-observed variable related to missingness.

However, we can assess whether MCAR is satisfied – the condition required for our per-protocol analysis. To do so, we will test for associations between all covariates and missingness with t-tests, chi-square tests, and/or Fisher's exact tests, as appropriate. The results of the logistic regression model predicting missingness based on the combination of covariates will also be reported and discussed.

6.6. Interim Analyses and Data Monitoring

There will be no planned interim analyses for efficacy or futility conducted for this study, but the DSMB may modify this during ongoing safety monitoring. The study team will review all adverse events by cumulative reports on a monthly basis. Adverse events will be graded using the protocol defined grading system. The DSMB, established by the study team, will monitor this study.

The DSMB will review the safety data when the study reaches 50% enrollment (i.e. 34 subjects enrolled per parasite group). The DSMB will review safety data after the 68th subject completes visit 8.

Asymptomatic subjects (34) enrolled under Version 1-4 of the protocol will have their data reviewed and clinical database locked for analysis first and a separate report generated. This may be generated before follow-up is completed in the symptomatic study population.

In the event that recruitment and follow-up for either the Giardiasis arm or the Amebiasis arm is completed ahead of the other, the primary and secondary endpoints may be analyzed for that arm using the specified methods. This report will be considered the interim CSR and will contain detailed unblinded information about the participants, their immunological response to treatment as well as their side effects and any laboratory abnormalities. The interim CSR will be followed with a release of data corresponding to the report.

6.7. Multiple Comparisons/Multiplicity

For each study population (asymptomatic, symptomatic) and disease group (amebiasis, giardiasis) there is a single primary endpoint. This can be viewed as four parallel studies. No adjustments for multiple testing are planned.

7. STUDY SUBJECTS

7.1. Disposition of Subjects

[Table 14](#) will present a summary of the reasons that subjects were screened but not enrolled. The table will be repeated for each study population.

The disposition of subjects in the study will be tabulated by treatment group, separately for each disease group and study population ([Table 9](#) and [Table 10](#)). The table shows the total number of subjects screened, the number that enrolled and received at least 1 dose, the number that received all scheduled doses, and the number that completed stool sample for the primary endpoint (day 5 for the giardiasis group; day 7 for the amebiasis group).

A flowchart showing the disposition of study subjects, adapted from the Consort Statement (Drummond, 2001) is included ([Figure 3](#)). This figure will present the number of subjects screened, enrolled, lost to follow-up, and analyzed, by treatment arm. A separate flowchart will be created for each study population.

The composition of analysis populations, including reasons for subject exclusion, by treatment arm, is presented in [Table 11](#) and [Table 12](#). A separate table is provided for each disease group and study population.

[Listing 1](#) and [Listing 2](#) will include subjects who discontinued dosing or terminated from study follow-up, and the reason will be included. The listings will be displayed separately for each disease group and study population.

7.2. Protocol Deviations

A summary of subject-specific protocol deviations will be presented by the reason for the deviation, the deviation category, and treatment group for all subjects ([Table 8](#)), separately for each disease group and study population. All subject-specific protocol deviations and non-subject-specific protocol deviations will be included as data listings ([Listing 3](#), [Listing 4](#), [Listing 5](#), and [Listing 6](#), respectively).

8. EFFICACY EVALUATION

All efficacy analyses will be performed on the modified Intention-to-Treat (mITT) population, as described in section 4.3.1, as a primary analysis. As a secondary analysis, the analysis will be repeated on the per-protocol population, as described in section 4.3.2. All tests will be two-sided and will use a significance level of 0.05. No adjustments will be made for multiple testing. All results will be reported as point estimates (differences in proportions, odds ratios or mean differences across groups, as appropriate) and interval estimates (95% confidence intervals).

8.1. Primary Efficacy Analysis

8.1.1. Amebiasis Group

For the asymptomatic population, the primary amebiasis endpoint is clearance of *Entamoeba histolytica* by day 7, defined as no detection of cysts or trophozoites of *Entamoeba histolytica* or negative antigen detection on day 7. The differences in parasite clearance rates between the placebo and auranofin arms for *Entamoeba histolytica* will be reported, along with the odds ratio (OR) and their 95% confidence intervals. The confidence interval for the odds ratio will be computed using the assumption of asymptotic normality of the log odds ratio, which should hold in this case as sample sizes are 34 in each arm. The difference in proportions is normally distributed for large enough sample sizes unless one or both of the proportions being estimated is near the boundary of the parameter space (i.e., zero or one). We expect normality to hold as we expect 15-20% parasitological response in the placebo group and 80% in the treatment group, but if it does not, we will use the adjusted Wald estimate as recommended by Agresti and Coull [3].

If some subjects are missing their response value, multiple imputation, as described in section 5 above, will be used to adjust estimates of treatment effect and standard error.

The following hypotheses will be tested:

H_0 : The probability of parasitological response by Day 7 for subjects receiving auranofin is equal to that for those receiving placebo.

H_A : The probability of parasitological response by Day 7 for subjects receiving auranofin differs from that for those receiving placebo.

As a secondary analysis, multivariable logistic regression analysis will be performed to study the association between clearance rates and intervention arm, adjusting for baseline demographic and clinical characteristics. A series of models will compare each baseline covariate with treatment status and the response. Baseline variables will include demographic variables, baseline vital signs and laboratory values. Covariates that are significantly associated with both treatment group and outcome ($p < 0.10$) will be selected as predictors in a multivariable logistic regression model as these are possible confounding variables. The logistic regression model assumes that continuous covariates are linearly related to the log odds of the response. To test this assumption, we will calculate the empirical log odds of the response repeatedly for different observed intervals of the covariate (e.g., calculate the empirical log odds when the covariate is valued 0-5, 5-10, 10-15, etc.), and plot the empirical log odds against the covariate interval. If the linearity assumption holds, this graph will show an approximately linear pattern. Transformations (e.g. the log transformation) for continuous covariates showing a nonlinear relationship to the response will be considered.

[Table 18](#) and [Table 20](#) will present the numbers and proportions (with 95% confidence intervals) of subjects with parasitological response by Day 7 for the treatment and placebo arms in the amebiasis strata for the

asymptomatic and symptomatic populations, respectively. These tables also present the difference in proportions between treatment and placebo groups and odds ratios, with their 95% confidence intervals. Separate versions of the tables will be provided for the modified-Intention-to-Treat population and the Per-Protocol population.

In the symptomatic population, the primary outcome is resolution of diarrhea by Day 7. This variable will be analyzed with the same approach above described for the analysis of parasitological response in the asymptomatic population. The following hypotheses will be tested:

H_0 : The probability of resolution of diarrhea by Day 7 for subjects receiving auranofin is equal to that for those receiving placebo.

H_A : The probability of resolution of diarrhea by Day 7 for subjects receiving auranofin differs from that for those receiving placebo.

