5. SAMPLE SIZE CONSIDERATIONS

The primary amebiasis outcome for this study is to compare the proportion of patients/subjects with resolution of diarrhea by Day 7 of therapy, in which placebo is expected to have a clearance rate of approximately 15-20%. Sample size calculations for both primary endpoints are based on a two-sample, two-sided binomial test for proportions, with alpha set to 0.05. Calculations were performed using the R statistical package (Version 3.0.2; <http://www.r-project.org>). The primary amebiasis endpoint in this aim is to compare the resolution of diarrhea between the two study arms to demonstrate that auranofin increases resolution of diarrhea. For this power analysis, we assume the following: a predicted diarrhea resolution rate of at least 80% (based on treatment results with current standard therapy with metronidazole [1]) in the auranofin treatment group.

With these assumptions, assuming 10% attrition (determined from the average of multiple other clinical trials in the same Mirpur district), a sample size of 68 with amebiasis (34 per arm; 60 completers in total) achieves greater than 95% power to detect a difference between the group proportions of 60%. The high statistical power for the primary endpoint is planned to also ensure adequate power for the secondary endpoints.

For the primary giardiasis endpoint of proportion of subjects with clearance of Giardia by Day 5, a similar sample size of 34 per arm will achieve 85% power to detect a 40% difference between treatment arms with a predicted clearance rate of 70% (based on response rates to metronidazole or tinidazole, Gardiner, 2001) and a 30% clearance rates in placebo.

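### The normal-approximation interval for the primary difference in proportions covers about 93%, not 95%, at the amebiasis rates that the SAP uses to justify it

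*SAP*

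**What the plan says.** SAP 8 promises point estimates with "interval estimates (95% confidence intervals" for all efficacy results. SAP 8.1.1 then sets out two approximations for the primary comparison.

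- For the odds ratio it assumes a normal log odds ratio, "which should hold in this case as sample sizes are 34 in each arm".
- For the difference in proportions it treats the estimate as normal in large enough samples unless a proportion lies close to zero or one. It adds: "We expect normality to hold as we expect 15-20% parasitological response in the placebo group and 80% in the treatment group". If normality fails, an adjusted Wald estimate is to be used. No threshold or test defines failure, and the adjustment is not written out for a difference of two proportions.

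That text is written for the asymptomatic group. For resolution of diarrhea in symptomatic amebiasis the SAP says: "This variable will be analyzed with the same approach above described for the analysis of parasitological response in the asymptomatic population". SAP 8.1.2 applies analogous methods to giardiasis. The shells for Tables 20 and 21 take the p-value from Fisher's exact test and leave the interval method to a footnote still to be written.

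**The concern.** The SAP's reason for not using the adjusted interval is that 15-20% and 80% are far enough from the boundary. With about 30 to 34 subjects per arm, that needs checking. The plain Wald interval for a difference can fall short of its nominal level well before a proportion reaches zero or one.

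At stake is the interval around the main effect estimate. If it covers 93%, it misses the true difference about 7 times in 100, not 5. The fallback would not correct this, because the plan states in advance that the expected rates do not call for it. A switch without a threshold also leaves the choice of a primary interval to be made after the data are seen.

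**Working it through.** **Inputs**
- Interval: two-sided 95%, z = 1.96 (SAP 8).
- Rates: auranofin 80%, placebo 15-20% (SAP 5 and 8.1.1). Giardiasis: 70% vs 30% (SAP 5).
- Size: "a sample size of 68 with amebiasis (34 per arm; 60 completers in total"), so 34 per arm randomized and, assuming an even split, 30 per arm completing. SAP 5 reaches this "assuming 10% attrition" (68 × 0.90 = 61.2, close to 60).

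**Plan's own figure.** The SAP gives no coverage figure beyond the nominal 95%, so I checked the inputs against its power statement. That statement uses a "two-sample, two-sided binomial test for proportions, with alpha set to 0.05", and says the design "achieves greater than 95% power to detect a difference between the group proportions of 60" percentage points. At 30 per arm and 80% vs 20%:

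(0.60 − 1.96 × √(2 × 0.5 × 0.5 / 30)) / √(2 × 0.8 × 0.2 / 30) = (0.600 − 0.253) / 0.103 = 3.36, which gives power of 99.96%.

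Fisher's exact test gives 99.8%. Both agree with the statement.

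**Coverage.** With x1 and x2 successes among n per arm:
- Plain Wald: d = x1/n − x2/n, with limits d ± 1.96 × √[p1(1−p1)/n + p2(1−p2)/n], where p1 and p2 are the observed proportions.
- Adjusted Wald (+1/+1): the same formula with (x + 1)/(n + 2) for each proportion and n + 2 for each n.
- Exact coverage: the sum of Bin(x1; n, π1) × Bin(x2; n, π2) over all tables whose interval contains π1 − π2.

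| Per arm | True rates | Plain Wald | Adjusted +1/+1 | Adjusted +2/+2 | Newcombe score |
|---|---|---|---|---|---|
| 34 | 80% vs 20% | 93.1% | 96.2% | 94.6% | 94.8% |
| 34 | 80% vs 15% | 93.5% | 95.4% | 92.0% | 94.4% |
| 30 | 80% vs 20% | 91.9% | 96.3% | 94.5% | 94.5% |
| 30 | 80% vs 15% | 94.1% | 95.9% | 94.4% | 93.7% |
| 34 | 70% vs 30% | 94.8% | 95.1% | 95.9% | 95.2% |
| 30 | 70% vs 30% | 94.2% | 94.7% | 95.7% | 94.9% |

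Coverage of this kind jumps as the rates shift slightly, so single points can mislead. Averaged over 75-85% vs 15-20%, plain Wald covers 93.3% at 34 per arm and 93.1% at 30. It was below 95% at every grid point. The +1/+1 version averages 95.3-95.4%.

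**Width or centre.** Expected widths, plain vs +1/+1:
- 34 per arm, 80% vs 20%: 0.373 vs 0.375.
- 34 per arm, 80% vs 15%: 0.353 vs 0.358.
- 34 per arm, 70% vs 30%: 0.429 vs 0.422.

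Take 27/34 vs 7/34 observed:
- Plain: 0.588 ± 0.192, or 0.396 to 0.780.
- Adjusted: 28/36 − 8/36 = 0.556, ± 0.192, or 0.363 to 0.748.

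Both intervals are 0.384 wide. The adjusted one sits closer to zero.

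**The case against.** The strongest reply is that little depends on this. The p-value comes from Fisher's exact test. At 80% vs 20% and 30 per arm, the probability that the lower limit exceeds zero is 0.9992 with either interval. The primary conclusion would not change, and that part of the reply stands in full.

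Three further points also stand in part.

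- The SAP never names plain Wald as its default. The reading rests on the appeal to normality, on the named fallback being the adjusted form of Wald, and on SAP 6.5, which computes a difference and its standard error. It is a strong inference, not the text.
- The SAP already holds the remedy in reserve. What it lacks is a rule for using it, and the one statement it makes on the matter points away from using it at the expected rates.
- The 30-per-arm figures describe a complete-case analysis. The primary analysis uses the mITT population with multiple imputation, so 34 per arm is the closer guide.

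A reader might infer that the intervals are simply too narrow. The widths above do not support that. A reader might also extend the 93% to giardiasis or to the secondary proportions. At the giardiasis planning rates coverage is 94.2-94.8%, and the SAP gives no planning rates for the secondary proportions.

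**Conclusion.** The concern holds, at modest size, for the amebiasis primary endpoint. At the rates the SAP cites, the nominal 95% interval covers about 93%: 93.1-93.5% at 34 per arm and 91.9-94.1% at 30. The SAP's stated reason for relying on normality therefore fails at its own inputs, and the untriggered fallback does not repair it. The fault lies mainly in the centring of the interval. It affects the reported interval only, not the test.

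The result rests on four assumptions: plain Wald is the default, the true rates are near the planning values, the arms are equal, and the responses are complete and binomial. Coverage after multiple imputation was not computed.

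A reader might infer a much larger shortfall in the asymptomatic group, since SAP 6.2 reports only 34 such subjects in all while 8.1.1 speaks of 34 per arm. The mismatch is real. However, the split by disease and arm is not given, so the documents support no specific coverage figure there.

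**What to change.** In SAP 8.1.1, delete the conditional switch and prespecify one interval for every difference in proportions, used unconditionally. Either of these will do:

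- adjusted Wald with one success and one failure added to each arm, with the formula written out. The version must be stated, because adding two and two covers only 92.0% at 34 per arm for 80% vs 15%;
- a score-based interval such as Newcombe's, which covers 93.7-94.8% at the amebiasis rates.

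Keep the unadjusted risk difference as the reported estimate. The adjusted centre should serve only to build the interval, since reporting it would shrink the effect (24/30 vs 6/30 is 0.600 unadjusted and 25/32 − 7/32 = 0.563 adjusted). With multiple imputation, compute the adjusted centre and standard error in each completed data set and combine those for the interval. Pool the unadjusted differences separately for the estimate. If a score interval is chosen, the SAP must also say how it is combined across imputations.

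Name the method in the footnotes of Tables 18-25 and 28-34, and note there that the estimate need not be the midpoint of the interval.

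The cost is a few sentences in the SAP and a small program change. Expected widths change by at most about 0.007 in the 34-per-arm cases shown.

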11.4 Final Analysis Plan

Analysis Plan for Primary Outcomes. The primary amebiasis endpoint is resolution of diarrhea by Day 7. Parasite clearance rates between the placebo and auranofin arms for *Entamoeba* will be compared using a Fisher's exact test for proportions. Differences in the rates between the two groups, along with the odds ratio (OR) and their 95% confidence intervals will be reported. As a secondary analysis, multivariable logistic regression analysis will be performed to study the association between clearance rates and intervention arm, adjusting for baseline demographic, stratification variables, and clinical characteristics. Variables significantly associated with both treatment group and outcome ($p < 0.10$) will be included in a multivariable logistic regression model as covariates. There will be no planned interim analyses for efficacy or futility conducted for this study, but the DSMB may modify this during ongoing safety monitoring.

Similarly, for the giardiasis primary endpoint, methods analogous to the amebiasis primary endpoint will be used to determine the resolution of diarrhea by Day 5.

Analysis Plan for Secondary Outcomes. The secondary outcome measures are: *Entamoeba*: Proportion of subjects with positive EIA for *E. histolytica* and positive smear for trophozoites on enrollment with parasitological response (no detection of trophozoites on microscopic exam) by Day 7; proportion of subjects with positive EIA for *E. histolytica* and positive smear for trophozoites on enrollment with parasitological response (no detection of trophozoites on microscopic exam or negative antigen detection) by Day 3 and 5; rate of decrease of trophozoite/cyst load by qPCR in stools by Days 3, 5 and 7; proportion of subjects with negative stool antigen test by Days 3, 5, 7, and 14; proportion of subjects with sustained cure (no detection of trophozoites by microscopic exam) at 14 and 28 days; and the proportion of subjects with relapse (same strain) or re-infection (new strain) with positive stools at Days 14 and 28 by genotyping the initial vs. subsequent strain, and time to resolution of diarrhea.

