9. SAFETY EVALUATION

9.1. Demographic and Other Baseline Characteristics

Summaries of age, sex, ethnicity, and race will be presented by treatment group and overall ([Table 15](#) and [Table 16](#)), for each disease group and study population. Ethnicity is categorized as “Hispanic or Latino”, or “Not Hispanic or Latino”. In accordance with NIH reporting policy, subjects may self-designate as belonging to more than one race or may refuse to identify a race, the latter reflected in the CRF as “No” to each racial option.

Individual subject listings will be presented for all demographics ([Listing 9](#) and [Listing 10](#)); pre-existing medical conditions ([Listing 11](#) and [Listing 12](#)); vital signs and oral temperature ([Listing 31](#) and [Listing 32](#)); and concomitant medications ([Listing 35](#) and [Listing 36](#)). These listings will be presented separately for each disease group and study population.

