9.6. Clinical Laboratory Evaluations

Laboratory parameters include white blood cell count, hemoglobin, hematocrit, platelets, BUN, Creatinine, AST, ALT, and urine protein, all measured during screening and on Study Day 7. Units and severity grading for the labs are summarized in [Table 7](#).

The distribution of laboratory results by maximum severity, study day and treatment group will be presented, separately for each disease group and study population, in [Table 46](#) through [Table 50](#). Abnormal laboratory results related to study treatment will be summarized by maximum severity, study day, and treatment group in [Table 51](#) through [Table 58](#), separately by disease group and study population. Descriptive statistics including mean, standard deviation, median, minimum and maximum values by study day, for each laboratory parameter, will be summarized separately for each disease group and study population in [Table 59](#) through [Table 66](#). Note that in general, summaries include only scheduled labs: unscheduled follow-up labs will be excluded from summaries but included in the listings. These include summaries at each time point as well as summaries in the change in observed values from baseline to Day 7. Listings of abnormal laboratory events (one listing for each disease group and study population) will be included in [Table 44](#) and [Table 45](#). Time trends of laboratory values will be graphically displayed in [Figure 22](#) and [Figure 23](#). Listings for all laboratory values will be provided, separately for each disease group and study population, in [Listing 25](#) through [Listing 30](#).

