9.7. Vital Signs and Physical Evaluations

Vital signs include height and weight, temperature, systolic and diastolic blood pressure, and pulse. These were assessed during screening and on every scheduled visit. Targeted physical exams were conducted on the same days and looked for abdominal pain, hair loss, urticaria, rashes, stomatitis, conjunctivitis, and glossitis. Refer to [Table 6](#) for vital sign grading criteria.

Vital signs will be tabulated by visit, severity, and treatment group, separately for each disease group and study population ([Table 67](#) through [Table 78](#)). Vital sign listings will be provided for subjects in the Safety population ([Listing 31](#) and [Listing 32](#)). Physical exam findings will be listed in [Listing 33](#) and [Listing 34](#).

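### The secondary adjusted model screens baseline covariates on chance association with the randomised arm, so it rarely adjusts for a real predictor and its odds ratio has no fixed meaning

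*SAP*

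**What the plan says.** SAP 8.1.1 plans, after the unadjusted primary comparison, a multivariable logistic regression as a secondary analysis. On the candidates it says: "Baseline variables will include demographic variables, baseline vital signs and laboratory values". It then admits "Covariates that are significantly associated with both treatment group and outcome", with p<0.10 as the threshold, on the ground that such variables may be confounders. Protocol 11.4 has the same rule: "Variables significantly associated with both treatment group and outcome".

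The rule reaches further than amebiasis. SAP 8.1.2 applies analogous methods to giardiasis, and SAP 8.2.1 does so for the binary secondary outcomes. The result has its own column, adjusted odds ratio with 95% CI, in Tables 18 to 21.

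Nothing elsewhere names a fixed covariate. SAP 6.4, headed Covariates and Subgroups, lists none. Protocol 11.4 mentions stratification variables among the adjusters, but the SAP text leaves them out, and Protocol 11.4 gives the SAP precedence where the two differ.

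**The concern.** Allocation is 1:1 at random within site and infection (Protocol 5.3.1, SAP 4.4.2). A baseline difference between arms is therefore chance, and a test of it does not detect confounding in the sense the SAP intends. Making that test a condition of entry has two effects. A covariate that truly predicts resolution is left out whenever the arms happen to be balanced on it, which is most of the time. And because treatment is expected to drive the outcome, an irrelevant covariate that differs between arms by chance tends to look associated with the outcome too, so it passes both screens more often than two independent tests would allow.

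At stake is the adjusted odds ratio printed beside the primary result. A logistic odds ratio is conditional on the covariates in the model, so what it estimates depends on which ones entered. The precision that adjustment could bring is mostly lost.

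**Working it through.** **Inputs from the documents.** 34 per arm and 60 completers in total per disease group; amebiasis 80% versus 15-20%; giardiasis 70% versus 30%; two-sided alpha 0.05 (Protocol 11.2, SAP 5). Screening threshold p<0.10 on both tests.

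**Candidate pool (assumed count).** The documents give types, not a number.
- Laboratory values, SAP 9.6: "Laboratory parameters include white blood cell count, hemoglobin, hematocrit, platelets, BUN, Creatinine, AST, ALT, and urine protein", which is 9.
- Vital signs, SAP 9.7: "Vital signs include height and weight, temperature, systolic and diastolic blood pressure, and pulse", which is 4 without height and weight.
- Demographics, SAP 9.1: "Summaries of age, sex, ethnicity, and race will be presented by treatment group and overall". I count age and sex, assuming race and ethnicity are nearly constant at these sites.

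That is 9 + 4 + 2 = 15, or 13 without hematocrit and urine protein.

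**1. The plan's own power figures.** The documents give no operating characteristic for the screen, so I reproduce what they do give. For giardiasis with 34 per arm, pooled z: power = Φ[(0.4 − 1.96·√(0.5/34)) / √(0.42/34)] = 92.8%. Fisher's exact test gives 87.6% at 34 per arm, 86.0% at 31 and 83.8% at 30, so the stated 85% fits Fisher with about 30-31 per arm. For amebiasis at 80% versus 20% with 30 per arm: 99.96% by z and 99.8% by Fisher, so the stated figure of more than 95% is met.

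**2. A strong predictor.** P(selected) = P(arm p<0.10) × P(outcome p<0.10, given that) ≤ 0.10, because randomisation fixes the first factor at about 0.10 whatever the prognostic strength. Simulation, 60-68 subjects, predictor with odds ratio 3 to 5 per SD (assumed):

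| Rates | OR 3 per SD | OR 5 per SD |
|---|---|---|
| 80% v 20% | 6.8-7.2% | 8.7% |
| 70% v 30% | 8.8-9.3% | 9.7-10.1% |

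**3. Site.** Stratified randomisation keeps arms close to balanced within site. With permuted blocks of 4 (an assumption; block size is not stated), site passed the arm screen in 0 of 5,000 simulated trials.

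**4. Irrelevant covariates.** Two independent tests would give 0.10 × 0.10 = 1%. But the test statistics against arm and against outcome are correlated, with correlation about φ = (p1 − p0) / (2√(p̄(1 − p̄))), where p̄ is the mean of the two rates. This is 0.40 at 70/30, 0.60 at 80/20 and 0.65 at 80/15. The bivariate normal probability that both exceed 1.645 in absolute value is then 1.9%, 3.1% and 3.5%, against 1.0% with no effect. Simulation agrees (20,000 trials per setting, t-tests or Fisher, covariates independent or correlated):

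| Rates | Each covariate | At least one of 13-15 |
|---|---|---|
| 70% v 30% | about 1.8% | 21-23% |
| 80% v 20% | about 3.0% | 31-36% |
| 80% v 15% | about 3.3% | 35-39% |
| no effect | about 0.9% | 11-13% |

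Check with 15 independent candidates: 1 − (1 − 0.0177)^15 = 23.5% and 1 − (1 − 0.030)^15 = 36.7%. A further simulation with 14 such covariates plus a predictor gave 23-25% at 70/30. With 9 candidates the figures fall to 15% (70/30) and 23-26% (amebiasis rates); with 17 they rise to about 28% (70/30) and 42% (80/20).

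**5. What adjustment would gain.** Power of the Wald test for treatment, 34 per arm:

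| Setting | SAP rule | Predictor pre-specified |
|---|---|---|
| 70/30, log-odds 1.0-1.5 per SD | about 91% | 96-98% |
| 70/30, log-odds 0.5 | 89.9% | 93.2% |
| 70/30, log-odds 0.25 | 89.7% | 91.8% |
| 80/20, log-odds 1.0 | 99.9% | 99.9% |

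Unadjusted power in the first row is 91-92%, so the SAP rule gains nothing over no adjustment. The weaker-predictor rows come from 1,500 trials each and are best read as gains of about 1-3 points.

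**6. Change of meaning.** At 70/30 the marginal odds ratio is (0.7/0.3)/(0.3/0.7) = 5.4. With a predictor of odds ratio 3 per SD, the true conditional log odds ratio is 2.10, an odds ratio of exp(2.10) = 8.2. Simulated medians were exp(1.75) = 5.8 without the predictor and exp(2.17) = 8.8 with it. The same table column would report one or the other according to chance imbalance.

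**7. Type I error.** Rejection under the SAP rule with no drug effect was about 3-5% across runs.

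**The case against.** The strongest reply is that this is a supportive analysis. SAP 6.5 states that the primary analysis includes no covariates. Tables 18-21 report one p-value, from Fisher's exact test, and none for the adjusted odds ratio. That stands: the primary result and the sample size do not depend on this rule, and the power figures above describe a comparison visible only through the adjusted confidence interval.

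The benefit also depends on assumptions. The documents say nothing about how strongly any baseline variable predicts resolution. At the amebiasis rates there is no power to gain, and with a weak predictor the gain is small. That stands too.

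Four stronger readings are tempting and are not supported:
- That choosing the model on the same data inflates false positives. The null simulations show no inflation, and no failure of interval coverage has been demonstrated.
- That a given irrelevant covariate enters in a quarter to a third of trials. Those figures are for at least one of an assumed pool at the planned effects; a single one enters in about 2-3.5%.
- That the plan excludes baseline stool frequency. The SAP speaks of demographic and clinical characteristics, and its list of what will be included need not be exhaustive.
- That stool count can simply be added. Eligibility is a threshold of three or more loose stools, diarrhea is self-reported, and Listings 16 and 18 have one diarrhea column. If only yes or no is held, the variable is constant in the mITT population, because SAP 6.3.1.1 removes those without diarrhea at enrollment.

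What remains untouched is the logic: the roughly 10% ceiling follows from randomisation and the threshold alone, and no other section repairs the rule.

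**Conclusion.** The two-way screen should go, as a free improvement of minor to moderate weight. It defeats the purpose of adjustment: a strong predictor (assumed odds ratio about 3-4.5 per SD) is adjusted for in about 7-10% of trials, the stratification factor almost never, and at least one irrelevant covariate in about 21-25% (giardiasis rates) or 31-39% (amebiasis rates). The last two figures rest on an assumed 13-15 candidates and on the planned drug effects; with no effect they fall to about 12%.

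The harm is confined to the secondary adjusted odds ratios. A reader might infer that the primary conclusion is at risk or that adjustment would help everywhere; neither follows. The worthwhile power gain is in giardiasis, and only if a strong predictor exists. The gain that does not depend on such a predictor is an adjusted odds ratio whose model is known in advance.

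**What to change.** In SAP 8.1.1 and 8.1.2 and in Protocol 11.4, delete the p<0.10 screen against treatment and outcome. Replace it with one pre-specified logistic model per symptomatic disease group containing treatment, site and age, fitted whatever imbalance is observed. Site restores the stratification variables that the Protocol names and the SAP drops; omit it if a single site fills the group. Add baseline loose-stool count only if the sponsor confirms, before unblinding, that the count itself is recorded and not just yes or no.

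Name the same covariates in SAP 6.4, use them for the binary secondary outcomes, and list them in the footnotes of Tables 20 and 21. Tables 18 and 19 carry the same column for the 34 asymptomatic participants, so the edit should also say what, if anything, is reported there.

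The cost is wording in two documents. It needs no new data or change in conduct if stool count is left out, and it replaces a series of screening models with one model per group.
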